## **5. Study procedures**

The study will be integrated into the MOUs. Women will be recruited directly from antenatal care. We will train existing counsellors, nurses and midwives in PrEP treatment (including risks and benefits) and the study. A trained recruiter will recruit directly from women at their first ANC visit, and if interested and eligible after the screening process, the women will go to the study space (Hanover Park) or study trailer (Green Clinic) in Gugulethu for the consent and study enrolment procedures. Consented, enrolled women will be invited to return every 3 months for study visits that correspond with their next ANC visit. All study staff will be trained, salaried staff working for UCT.

The purpose of the study visits will be to evaluate the study objectives. Below are the detailed steps for patient recruitment, enrolment, consent and study participation (Figure 5).

### For enrolment/baseline visit

**Step 1:** Health care providers in Gugulethu and Hanover Park MOUs provide group counseling to women at their first ANC visit, beginning with a session orientation, so that the patients know what to expect from the ANC service. This includes information about HIV testing and counselling, ART treatment for PMTCT, and the importance of HIV prevention for those women who test HIV-negative. The counselor will also be trained to provide simple information about PrEP, including what PrEP is, its benefits and risks, and the importance of daily adherence. The counselor will discuss the side effects that may occur in the first 1-2 weeks (similar to new ART patients) and will answer any questions about PrEP in the group setting.

**Step 2:** Following the South African National guidelines, patients privately receive pre-test counseling for HIV, including conducting a risk assessment and assessing her level of concern about having HIV. A discussion follows about the client's most recent risk exposure or behavior before and during pregnancy. The patient again is counseled about how best to reduce the risk of acquiring HIV during pregnancy (and increased risk of MTCT), including previous risk reduction attempts, successful experiences in using condoms, knowledge of partner's serostatus, obstacles to risk reduction, and triggers and situations that increase the likelihood of high-risk behavior.

**Step 3:** Disclosure of HIV negative result and post-test counseling. The counselor shows the client the actual results on the test kit, and then explores the client's reactions to the test results. Additional counseling will be provided with information about PrEP if the woman is diagnosed HIV-negative.

**Step 4:** The counselor explains that the mother may be eligible to participate in a study of HIV prevention in pregnancy and breastfeeding periods, including PrEP for women who decide they want to take it. The counselor will review the benefits and risks of using PrEP and participating in the study and will conduct a screening questionnaire.

**Step 5: Screening and study consent process:** If the client agrees to participate in the study (*she does not have to agree to take PrEP*), she will be referred to the study recruiter on site where the study counselor will review the **screening consent form** to evaluate study eligibility (see study inclusion, exclusion criteria). Following affirmative answers on the screening consent form the counselor will conduct a rapid HIV test, to test for acute HIV infection using an antigen/antibody test, and a Hepatitis B surface antigen test. Women who test positive for HIV (antigen, antibody or both) and/or Hepatitis B are ineligible for the study and will be referred to the clinic nurse for treatment and care.

All participants who are eligible for the study and agree to participate in the study will receive the study consent form and listen to/watch the consent form on a previously recorded video in Xhosa to ensure that she understands the study design and consent form before signing, asking questions to ensure comprehension.

**Hepatitis B infection (all women at screening):** The blood draw will also be used to test for active Hepatitis B infection using Hepatitis B surface antigen (HBsAg). Women who test HBsAg+ will be excluded from the study and referred for care according to national protocol

- **In addition, we will draw 1ml of serum to be frozen for testing in the case of discrepant results between the Determine HBsAg+ and NHLS laboratory results.**

**Infant consent form:** The participant will review and sign the infant consent form when she returns for her first post-partum visit with her infant.

**Step 6:** Participants will self-collect two vaginal swabs for storage: (1) for laboratory STI testing and (2) for vaginal microbiome analysis. Results for STI testing will be provided in 2-3 weeks after analysis and participants will be called in with STI+ results for treatment and partner referrals

**Step 7:** All participants will complete the baseline survey, which may take approximately 30-45 minutes to complete.

**Step 8:** The participant will receive individual counseling about HIV prevention in pregnancy including PrEP. Risk reduction counseling will be provided for all women and will include:

- **Consistent and correct use of condoms**
- **Knowing your status and partner's status**
- **If partner is HIV infected, should be on ART and achieve viral suppression**
- **Use of drugs and alcohol increases risk of HIV**

**Step 9: For all participants who decide to take PrEP, the study nurse will draw blood to test for baseline creatinine tests**

- Women with low creatinine can participate in the study but can only receive PrEP if their eGFR >60mL/min
- Test results will be received in 24-48 hours. If eGFR <60mL/min then the nurses will call participant to return and immediately stop using PrEP until they have a normal creatinine result (can return in following month)

**Step 10:** Participants who opt to take PrEP will receive counselling on the risks and benefits of PrEP. Following the counseling they will be asked: “Do you want to start taking PrEP today to prevent HIV? You will need to take it daily for it to be effective.” Her response will be recorded.

If yes:

1. The nurse will provide the participant with a 1-month supply of TDF-FTC and invite her to return in 1 month for her next study visit (after then they will receive 3 months prescriptions to correspond with their quarterly PrEP-PP study visit).
2. Nurses will provide contact information to the participant and ask her to call to report any side effects or adverse events while on PrEP, and nurse will track and report serious adverse events to study PIs, Pediatrician, and Obstetrician to decide on how to treat women and infants who have adverse events.

If she says she does not want to start PrEP, woman will be in the deferred PrEP arm:

1. The nurse will schedule her to return in 3 months for the follow-up study visit

**Step 10:** Participants will receive study staff contact information, instructions to call with any questions, and will be scheduled for their next visit in 1 month if on PrEP, or 3 months if not on PrEP, for the next study visit

**Step 11:** The study counselor will provide the mother with an appointment card and invitation for her partner to return to receive couples' HIV testing and counseling (if in a relationship). The session will end by encouraging the client to implement her/his risk-reduction plan (including PrEP if applicable and consistent condom use, couples testing) to prevent HIV acquisition.

**Step 12:** The participant will receive a snack and reimbursement for her time and transportation (up to R250 in a Shoprite voucher, refreshment and reimbursement for transportation) which is in line with our ongoing research at these sites. Further, we will combine the study visits with existing ANC or post-partum/well-baby visits to minimize the travel to the facilities outside of normal clinical checkups.

2. For follow up return visits:

Follow up visits will be at 1 month after baseline (to coincide with ANC visits) then after two months after birth then every 3 months thereafter (to coincide with post-partum, well-baby visits).

COVID update: During the COVID-19 lockdown, we will offer women the option of participating in interviews over the phone with participants who are willing and unable to attend the study visit. The interviewer will be in a private room and will ask the participant to be in a private, quiet space. The interviewer is an experienced isiXhosa -speaking research assistant and interviews will be conducted over the phone while the interviewer collects the data on the tablet using RedCap. Updated processes include:

- **Calling participants who miss study visits to assess if they wish to participate a phone interview (and schedule a time when they can be alone in a quiet place for 20-30 minutes)**

The interviewer will ascertain the participant ID and date of birth to ensure that they are speaking with the participant.

**Step 1:** In ANC: Healthcare providers provide counseling on HIV prevention and treatment at each ANC visit including HIV testing, as part of standard of care. In post-natal care and well-baby visits women may not receive regular HIV testing and messages and will receive this within step 2 (with study counselor). Following their ANC visit, enrolled women will be invited to attend the study site in each MOU to do the follow-up visit including the survey and prescription and adherence counseling (if on PrEP).

**Step 2:** Survey at each visit in a private study room

**Step 3:** In the study room, the study counselors will provide PrEP-specific counseling including adherence counseling for those on PrEP (and management of side effects), or counseling about the risks and benefits of PrEP for women not yet on PrEP. Women not on PrEP will be asked if they are interested in starting PrEP at this visit.

**Step 4:** *For participants on PrEP*, the study nurse performs a blood draw for creatinine clearance and a finger prick for DBS testing for adherence measures and (if applicable for this visit). See Table 1 for study calendar.

**Step 5 (for women on PrEP):** At each visit the study counselor will ask, and record responses, all participants on PrEP about any side effects associated with TDF/FTC, including diarrhea, nausea, fatigue, headache and rash (which are seen in about 10% of participants during the initiation of therapy). We will encourage participants to contact the study nurse if they experience side effects between visits.

**PrEP retention methods to improve adherence:** Each study visit will include counselling from peer counsellors who will discuss the importance of retention and adherence to PrEP for effectiveness. We will adapt messages from ongoing PrEP studies conducted by co-I [name] and team. We will also provide participants with a brochure to take home that discusses retention, adherence and side effects of PrEP. Each visit will include group and individual counselling. Group counselling will be led by a mother who has successfully taken PrEP for 3+ months to guide a discussion about the importance of retention, reminders on how to take the medication daily and how to address side-effects (e.g. nausea, headaches, etc).

**Step 6:** PrEP provision (for 1 or 2 months) and appointment reminder

*Follow-up & retention:* Tracing information will be taken at the enrolment visit and updated at each study visit. Retention activities will focus on scheduled measurement visits. Following our established approach in this

setting, we will provide reminder calls to participants before their measurement visits, and initiate tracing, including home visits, for women who do not attend the measurement visit within one week of the scheduled visit.

*PrEP provision:* monthly for the first 3 months, and then 2-months intervals after that. Participants on PrEP will have regular monitoring with laboratory tests, including creatinine levels to check for changes in renal function and dried blood spots (DBS) for adherence measures. Those with HBsAg+ will be excluded from the study. We will test for HIV seroconversion at every study visit.

*In-depth interviews:* We will select 30 women at random among women on PrEP and 30 women will be randomly selected among those not on PrEP to participate in a 1-hour in depth interview (over the phone during the COVID-19 lockdown) at first post-partum visit and at study end. The interviewer will follow a semi-structured discussion to review decisions to take (or not take) PrEP, side effects, issues related to adherence, disclosure of PrEP to others, and relationship status with open-ended questions.

*In-depth interviews at end of study (n=45 women from PrEP-PP who used PrEP):* We seek to use qualitative methods to assess the acceptability of, as well as facilitators and barriers to, novel PrEP methods in development (e.g. long-acting PrEP methods such as injectable cabotegravir, the dapivirine vaginal ring, and differentiated PrEP delivery) among a subsample of n=20 postpartum women enrolled in PrEP-PP. In addition we will recruit n=28 women who used PrEP and reported alcohol use or IPV before or during pregnancy to understand risk factors and barriers to PrEP use in this population. The semi-structured interviews will take 20-30 minutes among women who used PrEP during pregnancy or postpartum.

Eligible, consenting women will receive up to R150 in grocery vouchers and refreshments for their effort in the study as well as transportation to the facility.

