#### **Laboratory tests in women on PrEP:**

- **Renal function (in all women on PrEP):** Blood draws for creatinine levels will be taken at baseline, 3-month follow-up and at the end of the study, as per SA HIV Clinician Guidelines [26].
  - At enrollment: women with eGFR<60ml/min will be excluded from the study
  - At 3-month follow up: Women will not be able to continue taking PrEP with an eGFR <60m/min but will be able to continue to participate in the study. If their creatinine results change at the following visit they will be eligible to start PrEP.
- **DBS:** Dried blood spots will be prepared from finger pricks every three months in women on PrEP to evaluate adherence.
  - DBS cards will be prepared and stored following standard protocols and stored at -80°C for analysis at the end of the study with the clinical pharmacoanalytic laboratory of [name] at UCT. Using techniques developed by [name] at University of Colorado [16] adherence will be defined as red blood cells containing TDF-DP  $\geq 40\text{ng/dl}$  which is indicative of daily dosing [16]. As supplementary measures of PrEP adherence, we will use self-reported items that we will adapt from previous studies (including visual analogue scales as well as 3-day, 30-day and last visit recall questionnaires) (22-25), and pharmacy refill records to compare objective versus subjective measures and report on the effectiveness of each measure in correlation to the true measures of TDF-DP. We will determine final dosing and measures following reporting from ongoing PK studies of pregnant women on PrEP (e.g. Impaact 2009).
- Two self-collected vaginal swabs will be taken at enrollment and at 1-month visit. These will be stored at -80°C at University of Cape Town until processing for STI testing (at 2-3 weeks) and end of study

for bacterial and viral metagenomic sequencing. Briefly this will include microbial DNA extraction and shotgun metagenomic sequencing as performed previously by the [name] Lab (Brown, BP Biorxiv 2019).

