PrEP retention	# of women on PrEP who return for study visits (do not miss more than 1 visit) / total # of women in active cohort who are prescribed PrEP= proportion of women on PrEP who are retained in PrEP study	Electronic provider log (REDCap)	Daily, analysis weekly
PrEP adherence-subjective	# of women taking PrEP, who self-report taking their medication daily (& pill count to confirm this) during periods of sexual risk over time / total woman-time on PrEP in active cohort = PrEP adherence rate (subjective)	Electronic provider log (REDCap)	Daily, analysis weekly
PrEP adherence-objective	# of women taking PrEP who have >80% levels at >40ng/mL TDF-DP (indicating dosing in past 24 hours) at 3 rd trimester, delivery, and 6 weeks postpartum (and during sexual risk periods during that time) / total woman-time on PrEP in active cohort = PrEP adherence rate (objective)	Lab analysis of TDF-DP measures	Quarterly
Secondary Outcomes			
Predictors of attrition at key steps in the PrEP cascade	Individual, pill/study and disease specific predictors of attrition	Study survey	Study survey: Every study visit
HIV outcomes	HIV testing data: HIV-uninfected, HIV-positive for mother and child (if mother seroconverts)	Electronic provider log (REDCap)	Every visit
Health outcomes and adverse events	Any side-effects, creatinine, any negative maternal or neonatal outcomes (for mother and infant)	Electronic provider log (REDCap)	During routine lab tests and visits

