## Sample size considerations

The projected sample size for the study is *1200 women enrolled from 1st ANC visit until 12-months postpartum (estimated mean of 18-months follow-up)*. This estimate is based on the following assumptions:

- (1) 60% of women will initiate PrEP during the study period (versus approximately 40% who will not);
- (2) Approximately 75% of women on PrEP will be retained in care at 12-months (defined as not missing >1 study visit among women on PrEP)
- (3) 70% of those retained in care (n=378) will adhere to PrEP during at-risk periods.

A sample size of 1200 women yields 80% power to detect identify a relative risk of 2.0 or greater in key covariates including age (<25 vs. >25 years), pregnancy and relationship status associated with PrEP initiation versus non-initiation. A sample size of 378 women (e.g. 70% of women retained in the study on PrEP will be adherent as measured by TDF-DP measures) yields 80% power to detect relative risks of 2.0 or greater associated with persistence in the cohort. The analysis will be based on women who complete the 12-month postpartum cohort follow up. We will use relative risk ratios performed at a two-sided  $\alpha$  level of 0.05.

## Statistical analysis considerations for AIMS 1 & 2

The primary analysis for *Aim 1* will focus on measuring the distribution of women across the PrEP cascade including: initiation, continuation and persistence. **PrEP initiation** will be based on a woman's uptake of PrEP and allow for stoppage and re-initiation; **PrEP continuation** will be defined as not missing >1 visit among those on PrEP (with separate analyses of PrEP stoppage). For **PrEP persistence** for women on PrEP we will measure both *perfect persistence* (i.e. level of objective persistence throughout pregnancy and breastfeeding periods) as well as "*prevention-effective*" persistence (i.e. persistence during times of sexual activity) in participants through objective and subjective measures to evaluate agreement between the two measures, and the level of under- or over-reporting. Primary persistence analyses will use objective measures (TDF-DP from DBS) taken on all those who enrolled and initiated PrEP; subsidiary analyses will consider (i) other persistence measures and (ii) multiple imputation for missing persistence data.

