- **Measurement of use of PrEP:** Conducted through alternate definitions of the main outcomes (e.g. persistence by self-report versus persistence by pharmacy refill), compared using measures of agreement and will be analyzed as independent models to contrast estimated associations.
- **Measurement of prevention-effective execution:** Execution refers to PrEP persistence during a time when at-risk sex happens. It is calculated by: number of doses reported, or recorded/number of expected doses based on HIV risk and PrEP initiation/discontinuation
- **Prevention-effective continuation:** Prevention-effective continuation describes the duration of PrEP use during periods of HIV risk and references the absolute time of use during pregnancy and breastfeeding periods. We will adapt the methodology from previous PrEP studies in SA including FEM-PrEP to create a semi-ordinal composite persistence score from blood specimens from DBS every 2-months.  
For *Aim 1*, each outcome will be described via cumulative incidences at fixed intervals (e.g., cumulative PrEP initiation by delivery) and incidence densities over time. The general statistical approaches to these outcomes are analogous; data will be described graphically, including product-limit graphs, with preliminary analyses based on standard approaches for rates and proportions.

For *Aim 1*, we will also describe the frequency of HIV outcomes, including maternal HIV acquisition and MTCT, and any laboratory or self-reported side effects (e.g. changes in creatinine or self-reported side-effects [GI symptoms, headache, and etc.]). Analyses will include pure-count and person-time approaches; for the latter, confidence intervals will be calculated following the method of Breslow and Day. We will also describe infant outcomes over time (including birthweight, gestational age at delivery, pregnancy loss and any infant illness, hospitalization or death). While we expect the frequency of adverse HIV-related outcomes to be low, we will

describe characteristics of women who did/did not acquire HIV, and consider further analyses using the approaches outlined above.

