**Table 1. Study measures for PrEP-PP for AIM 1**

Primary Outcomes	Measurement	Source	Frequency
PrEP initiation	# of women who initiate PrEP over time / total # of women in active cohort = proportion of women who initiate PrEP	Electronic provider log (REDCap)	Quarterly
PrEP continuation	# of women on PrEP who return for study visits (do not miss more than 1 visit) / total # of women in active cohort who are prescribed PrEP= proportion of women on PrEP who continue in PrEP study	Electronic provider log (REDCap)	Quarterly
PrEP persistence (subjective)	# of women reporting taking PrEP in $\geq 5$ out of last 7 days or $\geq 25$ out of last 30 days (self-reported)/ total woman-time on PrEP in active cohort = PrEP persistence rate (subjective)	Electronic provider log (REDCap)	Quarterly
PrEP persistence (objective)	# of women taking PrEP who have $\geq 600$ fmol/punch (~7 doses/week) from DBS TDF-DP at 3rd trimester, delivery, and 6 weeks postpartum (and during sexual risk periods during that time) / total woman-time on PrEP in active cohort = PrEP persistence rate (objective)	Lab analysis of TDF-DP measures	Yearly and end of study
Secondary Outcomes			
Prevention effective persistence	4. # of women reporting adherence to PrEP (as per PrEP persistence subjective measure)/ total woman-time reporting sexual activity in past 30 days	Electronic provider log (REDCap)	Quarterly
	5. # of women having TDF-DP in DBS (as per PrEP persistence objective measure)/ total woman-time reporting sexual activity in past 30 days	Lab analysis of TDF-DP measures	Yearly and end of study

Prevention effective continuation	# of women who don't miss any PrEP study visits/ total woman time reporting sexual activity in prior visit	Electronic provider log (REDCap)	Quarterly
Predictors of attrition at key steps in the PrEP cascade	Individual, pill/study and disease specific predictors of PrEP initiation, continuation and persistence	Study CRFs and in-depth interviews (month 7 and12) (mixed methods)	End of study
Healthcare provider attitudes and knowledge about PrEP in pregnancy	Provider knowledge about PrEP and barriers/facilitators to PrEP prescription in ante and postnatal care	In-depth interviews	Year 1 of study
HIV outcomes	HIV testing data: HIV-uninfected, HIV incidence in mother and child (if mother seroconverts) compared by PrEP use/non-use	Electronic provider log (REDCap)	End of study

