#### **Methods/Approach:**

- (1) **Primary outcome:** See **Table 1** for precise definitions of (1) PrEP initiation, (2) PrEP continuation, (3) PrEP persistence-subjective, and (4) PrEP persistence-objective
- (2) **Primary analysis:** Describe each outcome listed above via cumulative incidences at fixed intervals (e.g., cumulative PrEP initiation by delivery) and incidence densities over time. The general statistical approaches to these outcomes are analogous; data will be described graphically, including product-limit graphs, with preliminary analyses based on standard approaches for rates and proportions.
  - a. **PrEP initiation** will be modelled using a probit model (preferred to estimate risk factors for common outcomes) with individual-level covariates as fixed effects.
  - b. **PrEP continuation** will be examined using similar approaches; in addition, we will use time-to-event methods to estimate factors associated with time to loss (non-continuation) among women having initiated PrEP.
  - c. **PrEP persistence** will be modelled using mixed effects probit models as above and generalized estimating equations to examine the marginal effect of individual-level covariates on persistence during the study.
    - a. **Sub-group analysis:** we will analyze the primary outcomes by sub-groups including age (<25 and  $\geq$ 25 years), STI diagnosis, relationship status, pregnant/postpartum

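### The primary objective adherence outcome is defined inconsistently: its tabulated time points do not match the readable visit schedules, the DBS intervals or the primary analysis text

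*Combined protocol and SAP*

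**What the plan says.** **Outcome, restricted form.** Protocol Table 2 counts women meeting the TDF-DP criterion at third trimester, "delivery, and 6 weeks postpartum (and during sexual risk periods during that time) / total woman-time on PrEP in active cohort". SAP Table 1 uses the same points, "fmol/punch (~7 doses/week) from DBS TDF-DP at 3rd trimester, delivery, and 6 weeks postpartum", and the same denominator. The SAP's Study measures list repeats the three points. SAP section 2.4 sends the reader to its Table 1 "for precise definitions of (1) PrEP initiation, (2) PrEP continuation, (3) PrEP persistence-subjective, and (4) PrEP persistence-objective".

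**Outcome, unrestricted form.** The Aim 1 list at the front of the SAP gives the objective threshold with no time points. The SAP's analysis considerations for Aims 1 and 2 put perfect persistence into the primary analysis, meaning the "level of objective persistence throughout pregnancy and breastfeeding periods". Protocol section 6 says the same of adherence. Both apply the primary DBS analysis to everyone who enrolled and started PrEP.

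**Visits.** The return-visit text in protocol section 5 gives one visit a month after baseline, "then after two months after birth then every 3 months thereafter". The opening of section 5 has women return every three months. The SAP's template table for continuation and persistence lists months 1, 3, 6, 9, 12, 15 and 18.

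**DBS interval.** The protocol's laboratory section states: "Dried blood spots will be prepared from finger pricks every three months in women on PrEP to evaluate adherence". The SAP's Study measures section also has quarterly DBS. Protocol Table 1 says bi-monthly. Protocol section 6 and the SAP's analysis considerations build a composite score from "blood specimens from DBS every 2-months".

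**The concern.** An outcome that the SAP calls precisely defined should tell the analyst which sample counts, for which women, and over what denominator. Here the tabulated time points do not line up with the visits that can be read, and other parts of the same plan describe the outcome without those time points. Two analysts could follow the documents faithfully and report different primary results.

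Three things are at stake:

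- Assigning samples to delivery and six weeks would be an ad hoc decision made with the data in hand.
- Women who start PrEP late belong to the analysis population but may have no sample that can count.
- Cohort adherence is meant to feed the Aim 3 model, which treats pregnancy and breastfeeding as separate prevention periods. An estimate that ends at six weeks would say little about the second.

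**Working it through.** **1. The plan's own figure.** 1200 × 0.60 = 720 initiators; 720 × 0.75 = 540 retained at 12 months; 540 × 0.70 = 378 adherent. This reproduces the stated 378. These are women retained at 12 months and described as adherent by TDF-DP, and the analysis is said to rest on women completing 12 months postpartum. Neither matches a table whose last sample is at six weeks.

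**2. Postpartum visits against the outcome points.** One month is 365.25/7/12 = 4.35 weeks. The return-visit text gives postpartum visits at about 2, 5, 8 and 11 months:

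| Visit (months after birth) | Weeks after birth | Weeks after the last outcome point |
|---|---|---|
| 2 | 8.7 | 2.7 |
| 5 | 21.7 | 15.7 |
| 8 | 34.8 | 28.8 |
| 11 | 47.8 | 41.8 |

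All four fall after six weeks. The first could serve as the six-week sample if a window were stated, but none is.

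**3. Third trimester.** The return-visit text has one antenatal follow-up, a month after baseline. Mean follow-up of 18 months less 12 postpartum leaves about 6 antenatal months. Assuming birth at 40 weeks:

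- Enrolment falls at 40 − 6 × 4.35 = 13.9 weeks, and the one-month visit at 18.3 weeks.
- For 7 down to 4 antenatal months, the one-month visit falls at 13.9 to 27.0 weeks.
- Taking 28 weeks as the start of the third trimester, that visit qualifies only if enrolment is at 28 − 4.35 = 23.7 weeks or later.

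So many women would have no third-trimester study visit on that schedule. The three-monthly schedule could supply one: with 5 antenatal months, the month-3 visit falls at 31.3 weeks. The documents do not say which schedule governs.

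**4. Study-month schedules.** Visits every three months, or at months 1 to 18 as in the SAP template, are not anchored to birth. One may land near delivery or six weeks by coincidence, but not by design.

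**5. Late starters.** The SAP counts initiation at any time in the study, and women not on PrEP are asked again at follow-up visits. On the return-visit text, the first postpartum chance at a study visit is at 2 months. A woman who starts then is in the analysis population, yet all three outcome points have passed.

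**6. Denominator.** Both tables divide by total woman-time on PrEP, with no cut-off. The bracketed mention of sexual-risk periods does not extend the numerator, because it refers back to the same interval. Six weeks is 6/4.35 = 1.4 months, so up to 12 − 1.4 = 10.6 months of PrEP time per woman can enter the denominator with no possible numerator event.

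As an illustration, take two women who start at enrolment, have 6 antenatal months and meet the criterion. One stops at six weeks postpartum and contributes 1/(6 + 1.4) = 0.14 per woman-month. The other continues to 12 months and contributes 1/18 = 0.06. Continuing on PrEP lowers the tabulated rate.

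**The case against.** The strongest reply is that the calendar governing DBS is protocol Table 1, to which the follow-up steps refer, and its column headings cannot be read. It shows 16 columns with DBS marked in 9, more contacts than the return-visit text lists. PrEP supply is also described as monthly and then two-monthly, and the refill and DBS rows are marked in the same columns, so some sample would usually fall within about a month of any target date. Women are recruited on the intention to deliver at the study facility. This stands to the extent that a delivery contact cannot be ruled out, and for six weeks the demonstrable fault is a missing window rather than a missing sample. It does not settle the matter: the table is titled by study month, and no readable text describes DBS at delivery.

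A second reply is that the plan does look beyond six weeks. DBS collection continues, the mixed and GEE models address persistence during the study, and self-reported persistence, also primary, is tabulated to month 18. This also stands. A reader might infer from the table that the plan ignores the breastfeeding year, or might express six weeks as a share of that year. The documents do not support either: the restriction sits in the tabulated definition and not in the whole plan, the outcome samples points rather than covering an interval, and no breastfeeding duration is given.

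Third, choosing three time points is a legitimate design choice. That is so, but the plan does not hold to it.

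**Conclusion.** The primary objective outcome is internally inconsistent and cannot be applied as tabulated without decisions that the plan does not make. The tables restrict it to three points; the Aim 1 list and the primary analysis text do not. No readable schedule names a delivery or six-week visit or states a window, and two DBS intervals are in force, including within the SAP for the same composite score. Read literally, women starting PrEP after six weeks postpartum have no qualifying sample, and up to 10.6 months of PrEP time per woman is denominator only.

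A reader might go further and conclude that delivery and six weeks are unscheduled, or that no woman who starts postpartum can be classified. Neither follows. The first is blocked by the unreadable calendar headings. The second holds only for starts after six weeks and only under the tables, since the Aim 1 definition would classify such women.

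The third-trimester finding rests on assumed values for antenatal follow-up (6 months, range 4 to 7), birth at 40 weeks and a third trimester from 28 weeks. The main conclusion rests on comparing the texts and does not depend on these values. It should be corrected before the objective outcome is analysed.

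**What to change.** 1. Reconcile the visit calendar across the opening and return-visit text of protocol section 5, protocol Table 1 and the SAP visit template. State one DBS interval in the protocol's laboratory section, Table 1 and section 6, and in the SAP's analysis considerations and Study measures.
2. Restate the objective outcome identically in protocol Table 2, the SAP Aim 1 list, the SAP Study measures list and SAP Table 1: the proportion of women at or above the TDF-DP threshold at each scheduled DBS visit, with stated windows, from the antenatal visits through 12 months postpartum, among women who have initiated PrEP by that visit.
3. Keep third trimester, delivery and six weeks only as labelled windows mapped to actual DBS visits.

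The cost is an amendment to protocol and SAP wording. No new sampling is needed: DBS is already planned through follow-up, and the laboratory section has cards stored for analysis at the end of the study. Replacing the woman-time rate with visit-specific proportions changes the estimand's form, so the amendment should say so and be dated before the DBS results are examined.
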